5.5.1.1 Plasma Concentration and its PK Parameter Analysis

<Plasma Concentration>

Plasma concentrations for tazemetostat and ER-897387 will be summarized using summary statistics (n, mean, standard deviation [SD], median, minimum, and maximum) by nominal time points.

Plasma concentrations of tazemetostat and ER-897387 will be listed for each subject by nominal time points with actual sampling time.

<Plasma PK Parameter>

PK parameters will be derived by noncompartmental analysis using Phoenix WinNonlin software (version 6.2.1 or later) according to Eisai Non-compartmental Pharmacokinetic Analysis Manual (302-104.00-MNL) (NCA-MNL, hereafter).

The following PK parameters for tazemetostat and ER-897387 will be calculated.

After Cycle 0 Day 1 dosing (single dosing)

C_{max} , t_{max} , $AUC_{(0-12h)}$, $AUC_{(0-t)}$, $AUC_{(0-inf)}$, λ_z , $t_{1/2}$, MRT, metabolite to parent $AUC_{(0-inf)}$ ratio with and without molecular weight correction

The following PK parameters will be calculated for tazemetostat only: CL/F and V_z/F .

After Cycle 1 Day 15 dosing (multiple dosing)

$C_{ss,max}$, $C_{ss,min}$, $t_{ss,max}$, $C_{ss,av}$, $AUC_{(0-\tau)}$, $AUC_{(0-t)}$, $t_{1/2}$, λ_z , MRT, PTF, $R_{ac}(C_{max})$, $R_{ac}(AUC)$, R_{ss} , and metabolite to parent $AUC_{(0-t)}$ ratio with and without molecular weight correction

The following PK parameters will be calculated for tazemetostat only: CL_{ss}/F and V_z/F .

Other PK parameters may be calculated as appropriate.

Summary statistics will be tabulated for the PK parameters of tazemetostat and ER-897387. Summary statistics (n, mean, SD, median, minimum and maximum) will be presented for all parameters (apart from t_{\max} and $t_{ss,\max}$ where mean and SD are not required). In addition, geometric mean and %CV will also be presented for all parameters apart from t_{\max} and $t_{ss,\max}$.

PK parameters of tazemetostat and ER-897387 for each subject will be listed.

5.5.1.2 Urine Concentration and its PK Parameter Analysis

Urine volume and urinary concentrations of tazemetostat will be listed for each subject by nominal collection periods.

The following urinary PK parameters will be derived by SAS and/or Phoenix WinNonlin according to NCA-MNL.

After Cycle 0 Day 1 dosing and Cycle 1 Day 15 dosing

- Amount of tazemetostat recovered in urine ($A_{e(t1-t2)}$) by each collection interval
- Cumulative amount of tazemetostat excreted in urine through total collection period (A_e)
- Cumulative fraction of dose excreted in urine until end of collection interval
- Renal clearance (CL_R) [CL_R will be obtained as $CL_R = A_{e(0-t)}/AUC_{(0-t)}$]

Summary statistics (n, mean, SD, median, minimum and maximum) will be tabulated for the $A_{e(t1-t2)}$ and urinary PK parameters of tazemetostat by collection period.

Urinary PK parameters of tazemetostat for each subject will be listed.

5.5.1.3 Pharmacokinetic Data Figures

The mean plasma concentrations of tazemetostat and ER-897387 after Cycle 0 Day 1 dosing and Cycle 1 Day 15 dosing will be displayed on one figure in linear scale and semi-log scale using nominal time with SD (tazemetostat and ER-897387, respectively).

The mean plasma concentrations of tazemetostat and ER-897387 will be displayed respectively on one figure in linear scale and semi-log scale using nominal time with SD after Cycle 0 Day 1 dosing and Cycle 1 Day 15 dosing, after Cycle 0 Day 1, and after Cycle 1 Day 15 respectively.

The individual and mean plasma trough concentrations (Cycle 1 Day 3, Cycle 1 Day 8, Cycle 1 Day 15, Cycle 1 Day 22, and Cycle 2 Day 1) and concentrations of 12 h after dosing (Cycle 0 Day 1 and Cycle 1 Day 15) of tazemetostat will be displayed using the nominal day in linear scale.

Individual plasma concentration of tazemetostat or ER-897387 for all subjects after Cycle 0 Day 1 dosing or Cycle 1 Day 15 dosing will be displayed on the same figure in linear and semi-log scale using actual time respectively.

Plasma concentration of tazemetostat and ER-897387 after Cycle 0 Day 1 and Cycle 1 Day 15 dosing, after Cycle 0 Day 1, or Cycle 1 Day 15 dosing will be displayed on one figure for each subject in linear and semi-log scale using actual time respectively.

5.5.2 Pharmacodynamic, Pharmacogenomic, and Other Biomarker Analyses

CCI

5.5.3 Pharmacokinetic/Pharmacodynamic Analyses

Not applicable

5.6 Safety Analyses

All tolerability analyses will be performed on the DLT Analysis Set. The Safety Analysis Set will be used for all other safety analyses.

5.6.1 Extent of Exposure

The number of cycles/days on treatment, quantity of study drug administered will be summarized. Number of subjects with dose reductions and dose interruptions will be summarized. As for the subjects with any dose reduction, time to first dose reduction will also be summarized.

The actual dosing transition and duration of both study drug with tumor response is presented using swimmer plot.

5.6.2 Dose Limiting Toxicities

For the analysis set for DLT evaluation, The number and percentage of subjects with DLT will be calculated. DLT will also be summarized by Medical Dictionary for Regulatory Activities (MedDRA) preferred term (PT).

5.6.3 Adverse Events

The AE verbatim descriptions (investigator terms from the CRF) will be classified into standardized medical terminology using the MedDRA. Adverse events will be coded to the

MedDRA lower level term (LLT) closest to the verbatim term. The linked MedDRA PT and primary system organ class (SOC) are also captured in the database.

A treatment-emergent adverse event (TEAE) is defined as an AE that emerges during time from the first dose of study drug to 37 days after the subject's last dose, having been absent at pretreatment (Baseline) or

- Reemerges during treatment, having been present at pretreatment (Baseline) but stopped before treatment, or
- Worsens in severity during treatment relative to the pretreatment state, when the AE is continuous.

Only those AEs that are treatment-emergent will be included in summary tables. All AEs, treatment-emergent or otherwise, will be presented in subject data listings.

The TEAEs will be summarized. The number (percentage) of subjects with TEAEs will be summarized by SOC and PT. A subject will be counted only once within an SOC and PT, even if the subject experienced more than 1 TEAE within a specific SOC and PT. The number (percentage) of subjects with TEAEs will also be summarized by highest Common Terminology Criteria for Adverse Events (CTCAE) grade.

The number (percentage) of subjects with treatment-related TEAEs will be summarized by SOC and PT. Treatment-related TEAEs include those events considered to be related to study treatment. The number (percentage) of subjects with treatment-related TEAEs will also be summarized by highest CTCAE grade.

The number (percentage) of subjects with SAEs and TEAEs leading to death, discontinuation from study drug, study drug dose reduction or interruption will be summarized by SOC and PT. Subject data listings of all SAEs and AEs leading to death, discontinuation from study drug, study drug dose reduction or interruption will be provided.

The number (percentage) of subjects with TEAEs and treatment-related TEAEs will be summarized by SOC, PT and CTCAE Grade in Decreasing Frequency.

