**Tolerability and Safety Analysis:**

All tolerability analyses will be performed on the DLT Analysis Set. The number and percentage of subjects with DLT will be calculated. DLT will also be summarized per type of toxicity. The Safety Analysis Set will be used for all other safety analyses.

The number and percentage of subjects with all AEs and SAEs observed after the first administration of study drug will be summarized and listed by SOC, PT, and severity. Summary statistics will be presented for laboratory test values, vital signs, 12-lead ECG, LVEF parameters, and ECOG-PS. If needed, the changes from baseline will also be summarized.

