### 9.3.3 Removal of Subjects From Therapy or Assessment

The investigator or subinvestigator may discontinue treating a subject with study treatment or withdraw the subject from the study at any time for safety or administrative reasons. The subject may decide to discontinue study treatment or withdraw from the study at any time for any reason. The reason for discontinuation will be documented. If a subject discontinues study treatment, the subject will enter the Follow-up Phase and complete protocol-specified off-treatment visits and procedures unless the subject withdraws consent. If a subject withdraws consent, the date will be documented in the source documents. The CRF will be completed indicating the primary reason for discontinuation. In addition, the date of last dose of study drug will be documented on the CRF.

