#### 9.5.1.5.1 ADVERSE EVENTS AND EVENTS ASSOCIATED WITH SPECIAL SITUATIONS

An AE is any untoward medical occurrence in a subject. An AE does not necessarily have a causal relationship with the medicinal product. For this study, the study drug is tazemetostat.

The criteria for identifying AEs in this study are:

- Any unfavorable and unintended sign (including an abnormal laboratory finding), symptom, or disease found after the time of informed consent, whether or not considered

related to the investigational product (Note: Every sign or symptom should not be listed as a separate AE if the applicable disease [diagnosis] is being reported as an AE)

- Any new disease or exacerbation of an existing disease. However, worsening of the primary disease should be captured under efficacy assessments as disease progression rather than as an AE.
- Any deterioration in nonprotocol-required measurements of a laboratory value or other clinical test (eg, ECG or x-ray) that results in symptoms, a change in treatment, or discontinuation of study drug
- Recurrence of an intermittent medical condition (eg, headache) not present pretreatment (Baseline)
- An abnormal laboratory test result should be considered an AE if the identified laboratory abnormality leads to any type of intervention, withdrawal of study drug, or withholding of study drug, whether prescribed in the protocol or not

All AEs observed during the study will be reported on the CRF. All AEs, regardless of relationship to study drug or procedure, should be collected beginning from the time the subject signs the study ICF through the final observation visit. SAEs will be collected until the final observation visit. Subjects who fail screening primarily due to AE(s) must have the AE(s) leading to screen failure and its seriousness reported on the CRF.

Any laboratory abnormality considered to constitute an AE should be reported on the CRF. Abnormal laboratory values should not be listed as separate AEs if they are considered to be part of the clinical syndrome that is being reported as an AE. It is the responsibility of the investigator or subinvestigator to review all laboratory findings in all subjects and determine if they constitute an AE. Medical and scientific judgment should be exercised in deciding whether an isolated laboratory abnormality should be classified as an AE.

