3.2 Overall Study Design and Plan

This is a multicenter, single-arm, phase 1 study to assess tolerability, safety, PK and preliminary anti-tumor activity of tazemetostat in patients with relapsed or refractory B-cell

NHL.

This study will be conducted in the following 4 phases: Pre-treatment Phase, Treatment Phase, Extension Phase, and Follow-up Phase.

The Pre-treatment Phase will last no longer than 28 days and include a period to obtain informed consent, screening, enrollment and a baseline assessment. After screening assessments, the patient who meets the inclusion criteria and does not meet the exclusion criteria will be enrolled. The baseline assessment will be conducted within 3 days before the treatment in order to confirm that the patient continues to meet the inclusion criteria and does not meet the exclusion criteria before moving to the Treatment Phase.

The Treatment Phase consists of Cycle 0 (4 days) for tazemetostat single-dose oral administration and Cycle 1 of 28 days for tazemetostat twice daily (BID) oral administration on a continuous basis.

Considering visit schedule and safety, subjects will be hospitalized from Cycle 0/Day 1 (C0D1) to Cycle 1/Day 15 (C1D15). Based on the thorough evaluation of the data obtained on C1D15 and all safety data available, the investigator or subinvestigator will determine whether subjects can be treated on an outpatient basis. When subjects are considered to require extended hospitalization to ensure subject safety, they will be hospitalized from C1D15 onwards.

The Extension Phase consists of Cycle 2 of 28 days and later for tazemetostat BID oral administration on a continuous basis and lasts until discontinuation of study drug.

Subjects will discontinue study drug at the time of disease progression, development of unacceptable toxicity, subject's request to discontinue, withdrawal of consent, or study termination by sponsor.

Follow-up Phase consists of the evaluation at discontinuation which is performed within 7 days after the discontinuation of the study and a final observation which occurs 30 days (+7 days) after final administration of tazemetostat or initiation of a new anti-tumor therapy, whichever occurs early.

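### The SAP's 37-day post-dose TEAE window covers newly emerging AEs only; re-emerging and worsening AEs keep an undefined 'during treatment' limit

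*SAP*

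**What the plan says.** The TEAE definition in SAP 5.6.3 has three limbs.

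- New AEs: "A treatment-emergent adverse event (TEAE) is defined as an AE that emerges during time from the first dose of study drug to 37 days". Those 37 days run from the last dose, and the AE must have been absent at baseline.
- Re-emerging AEs: "Reemerges during treatment, having been present at pretreatment (Baseline) but stopped before treatment, or"
- Worsening AEs: "Worsens in severity during treatment relative to the pretreatment state, when the AE is continuous"

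The same section then sets the consequence: "Only those AEs that are treatment-emergent will be included in summary tables". AEs that are not treatment-emergent appear only in subject listings.

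Protocol 9.7.1.8.3 has the same three limbs, but with the timing 'during treatment' in each of them and no 37-day window. SAP Section 8, which lists changes from the protocol's planned analyses, does not mention the new window. The SAP's data-handling text (Sections 7 and 8.2) does not define 'during treatment' either. The programming rules are in separate documents (SAP Section 9).

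**The concern.** The SAP replaced 'during treatment' with an explicit window in one limb and left it in the other two. Whether a post-dose event is tabulated then depends on whether the AE was already present before dosing, and not on its grade or timing. The plan gives no reason for the difference.

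An illustration: a Grade 1 AE recorded between consent and first dose stays unchanged on drug and worsens to Grade 3 ten days after the last dose. On a literal reading it is not a TEAE. A new Grade 3 AE on the same day is one.

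What is at stake is the completeness of the TEAE tables by SOC and PT, by relationship and by highest grade. Safety is the first secondary objective. The primary endpoint is not at stake.

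**Working it through.** **1. The plan's own figure.** SAP 3.2 and Protocol 9.1.1.4 place the final observation 30 days (+7 days) after the last dose, or at the start of a new anti-tumor therapy if that is earlier. The latest day is 30 + 7 = 37. This reproduces the 37 days in the first limb, so that limb was set to match the latest final observation.

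**2. Would the affected events be in the data?** Yes. Protocol 9.5.1.5.1 collects all AEs from consent through the final observation visit, and CTCAE grades are reported for both increases and decreases in severity. A post-dose rise in grade is therefore recorded.

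**3. What 'during treatment' can mean.** It has no definition. Two passages suggest that it ends with dosing. Protocol 9.3.3 says that after stopping study treatment "the subject will enter the Follow-up Phase and complete protocol-specified off-treatment visits and procedures". SAP 3.2 separates follow-up from the dosing phases: "This study will be conducted in the following 4 phases: Pre-treatment Phase, Treatment Phase, Extension Phase, and Follow-up Phase". Neither passage sets an analysis window. The capitalised term Treatment Phase covers Cycles 0 and 1 only, so it cannot be the intended meaning; it would also drop AEs during Extension Phase dosing.

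**4. Classification.** This takes 'during treatment' as first dose to last dose, which is an assumption and the literal reading.

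| AE type | First to last dose | 1 to 37 days after last dose |
|---|---|---|
| New | TEAE | TEAE |
| Re-emerging | TEAE | not a TEAE |
| Worsening | TEAE | not a TEAE |

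As written, 4 of the 6 combinations count. With one common window, 6 of 6 count. The 2 that differ are both post-dose and both concern AEs present before dosing. Literal post-dose cover is 37 days for new AEs and 0 days for the other two types.

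If 'during treatment' is instead read as the 37-day window, all 6 combinations count and nothing is left out.

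**5. Scale.** The plan is for 6 DLT-evaluable subjects per cohort. Taking 6 treated subjects, one affected subject changes a PT or SOC row by 1/6 = 16.7 percentage points if that subject has no other TEAE in the row, and by 0 points otherwise. This is the step size for one subject, not an expected effect. The documents give no rate of post-dose worsening or re-emergence.

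**The case against.** The strongest reply is that exclusion is one reading of an undefined phrase. The SAP may have meant its new first-limb wording to spell out 'during treatment', with the bullets simply left unedited, and the unseen programming specifications may already apply one window. Much of this stands: the sponsor probably did intend one window, and the documents do not show that any event will be left out. It does not remove the point, because an edit made in one limb out of three invites the narrower reading in the other two, and nothing else in the SAP settles it.

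The effect is also limited. The clearest cases are AEs recorded between consent and first dose, within a Pre-treatment Phase of at most 28 days. Inclusion criterion 12 bars some carry-over AEs of Grade 2 or higher. Laboratory worsening can still appear in the TEMAV tables (SAP 5.6.4), and every AE is listed. With about 6 subjects and no statistical comparison, a reader of the listings can find each case.

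Two stronger readings are tempting, and the documents do not support them.

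- A reader might infer that the SAP's limb timing breaks the protocol synopsis, under which "all AEs and SAEs observed after the first administration of study drug will be summarized and listed by SOC, PT, and severity". But Protocol 9.7.1.8.3 already confines the summary tables to treatment-emergent AEs, using the same three limbs. That tension lies between the synopsis and the protocol body. A common window would not remove it, because baseline AEs that do not change would still be excluded.
- A reader might extend the gap to every current medical condition that worsens after the last dose. Protocol 9.5.1.5.1 counts as an AE "Any new disease or exacerbation of an existing disease". A post-dose exacerbation can therefore be read as an AE that was absent at baseline, which falls in the first limb with its 37-day window.

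**Conclusion.** The concern holds as a minor inconsistency in a stated rule. Read literally, SAP 5.6.3 keeps out of the TEAE tables an AE present before dosing that first re-emerges or worsens within 37 days after the last dose, while it counts a new AE of the same grade on the same day. SAP Section 8 does not disclose the changed window.

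The conclusion rests on reading 'during treatment' as ending with the last dose. That is the plain sense but not a certainty. The effect on reported incidence is likely small and cannot be quantified from the documents. The DLT endpoint, assessed in Cycles 0 and 1, is unaffected. It would go too far to say that safety data are lost or that exclusion is certain: the events stay in the listings, and the programming rules have not been seen.

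**What to change.** Apply the existing window to all three limbs of SAP 5.6.3: an AE is treatment-emergent if, from the first dose to 37 days after the last dose, it emerges having been absent at baseline, re-emerges having stopped before the first dose, or worsens in severity relative to baseline. List this in SAP Section 8 as a change from Protocol 9.7.1.8.3.

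Do not add a cut-off at final observation if earlier. Final observation can be brought forward by new anti-tumor therapy (Protocol 9.1.1.4), while SAEs judged related must still be reported afterwards (Protocol 9.5.4.1). Such a cut-off would therefore remove events that the first limb now counts.

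The cost is one SAP sentence, one programming condition and one line in Section 8. Reported TEAE incidence may rise slightly.

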5.6.4 Laboratory Values

Laboratory results will be summarized using Système International (SI) units, as appropriate. For all quantitative parameters listed in [Section 9.5.1.5.3 Safety Assessments \(Laboratory Measurements\)](#), the actual value and the change from baseline to each postbaseline visit and to the last observation will be summarized by visit using descriptive statistics. Qualitative parameters listed in [Section 9.5.1.5.3](#) will be summarized using frequencies (number and percentage of subjects), and changes from baseline to each postbaseline visit and the last observation will be reported using shift tables. Percentages will be based on the number of subjects with both nonmissing baseline and relevant postbaseline results.

CTCAE v4.03 will be used to identify subjects with treatment-emergent markedly abnormal laboratory values (TEMAVs). Except for phosphate, a TEMAV is defined as a post baseline

value with an increase from baseline to a grade of 2 or higher. For phosphate, a TEMAV is defined as a postbaseline value with an increase from baseline to a grade of 3 or higher. When displaying the incidence of TEMAVs, each subject will be counted once in the laboratory parameter high and in the laboratory parameter low categories, as applicable. TEMAVs will be summarized by study overall.

The following combination of abnormal laboratory tests will be presented in listing.

- Elevated AST or ALT lab value that is greater than or equal to 3X the upper limit of normal
AND
- Elevated total bilirubin lab value that is greater than or equal to 2X the upper limit of normal
AND AT THE SAME TIME
- Alkaline phosphatase lab value that is less than 2X the upper limit of normal

The measured values for quantitative data will be displayed over time using Box plot.

5.6.5 Vital Signs

Descriptive statistics for vital signs parameters (ie, systolic and diastolic blood pressure, pulse, temperature) and body weight and changes from baseline will be presented by visit.

The measured values will be displayed over time using Box plot.

5.6.6 Electrocardiograms

ECG assessments were performed at each visit. Descriptive statistics for ECG parameters and changes from baseline will be presented by visit.

Shift tables will present changes from baseline in ECG parameters and ECG findings.

In addition, the number (percentage) of subjects with at least 1 postbaseline abnormal ECG result in QTcF will be summarized. Clinically abnormal ECG results in QTcF will be categorized as follows:

Absolute QTcF interval prolongation:

- QTcF interval >450 ms
- QTcF interval >480 ms
- QTcF interval >500 ms

Change from baseline in QTcF interval:

- QTcF interval increases from baseline >30 ms
- QTcF interval increases from baseline >60 ms

